Design and conduct of AERCONN Preparation of protocol and revisions Preparation of CRFs Publication of study reports

Steering committee (SC) (PIs)

Responsibilities: Agreement of final protocol (approved 21-11-2013). Reviewing progress of study and if necessary approving changes to the protocol and/or investigators brochure to facilitate the conduction of the study.

Data Manager

[name] Maintenance of trial IT system and data entry Data verification

Data Monitoring and Safety Board (DMSB)

[name], [name]

II) Introduction

6 Background and rationale

6a: Description of research question and justification for undertaking the trial, including summary of relevant studies (published and unpublished) examining benefits and harms for each intervention

Historically, MS patients have been advised to refrain from physical exercise due to heat sensitivity of some symptoms. However, a first randomized controlled trial in 1996 demonstrated that exercise may have beneficial effects on quality of life. Since then, improved quality of life and walking ability in MS after exercise training has been confirmed in several RCTs. Based on preclinical evidence and first pilot studies in humans, this phase IIa will investigate whether exercise has beneficial effects beyond psychological well-being, namely improving cognitive function and related measures of brain connectivity.

Exercise may be "neuroprotective" in MS

Voluntary wheel running enhances hippocampal neurogenesis in animal models (Cotman et al 2007). Importantly, hippocampal damage has been linked to neuropsychiatric symptoms of MS such as depression and memory impairment (Gold et al in press; Gold et al 2010, Sicotte et al 2008; Kiy et al 2011), thereby presenting an important target brain region for neuroprotective therapies in MS. A mechanistic link between exercise and cognitive function has been provided by numerous animal studies indicating increased neuroplasticity and improved cognitive function (Cotman and Berchtold 2002). The underlying neurobiological mechanisms of this protective effect are poorly understood but may include several pathways such as neurotrophic factors (Cotman et al 2007), anti-inflammatory processes (Gleeson et al 2011) and myokines (Pedersen 2011; Pedersen and Febbraio 2012).

Several studies have reported a positive association between aerobic fitness and cognitive parameters in healthy adults (Smith et al 2010; Etnier et al 2006). In addition, exercise interventions appear to enhance cognitive function in both healthy individuals as well as subjects at risk of dementia (Hillman et al 2006; Schulz et al 2012).

Work by Prakash et al (2010, 2011) provided first cross-sectional evidence for differences in gray matter density and resting state networks in trained versus untrained MS patients. Further supporting the biological rationale for CNS effects of exercise in MS,

evidence from the animal model of MS, experimental autoimmune encephalomyelitis (EAE), suggests that exercise might directly affect pathology as some studies indicate disease attenuation through exercise (LePage et al 1996) as well as axonal protection and enhancement of neuronal plasticity (Rossi et al 2009). However, to date for the effectiveness of exercise interventions on neuroprotection merely does not exist. To date, only one study has explored effects of low intensity level exercise on cognitive function in MS patients with minor disability (Oken et al 2006) showing no clear-cut effects. We have recently conducted a pilot trial with n=40 MS patients in the progressive phase (EDSS 4-6) comparing an 8 week (20 session) training period with hand- and bicycle ergometry as well as rowing to a non-exercising waitlist control group. We could demonstrate not only a significant beneficial effect on walking ability but also on neuropsychological tests of attention and verbal learning (Briken et al 2013). In this small trial now provides the basis for studying the effects of exercise on brain structure and function using neuropsychological tests as well as CNS connectivity in the current study. Novel imaging markers of CNS connectivity

MRI is regarded the most promising tool to assess tissue integrity in the brain in MS. However, due to the slow nature of neurodegenerative processes and the limited sensitivity of conventional MRI surrogate markers, predictive short-term changes have not been established (Barkhof et al 2009). Although non-conventional MRI markers such as T2 subtraction, brain atrophy, DTI or MTR as well as lesion evolution (Barkhof et al 2009; van den Elskamp et al 2010) might detect some aspects of neuroregeneration, until now they seem not sensitive enough for short-term changes.

Measures of functional connectivity such as correlations in spontaneous brain activity provide powerful access to large-scale organizational principles of the central nervous system (Raichle 2010). These analyses may therefore provide a more sensitive tool to detect regeneration and repair. Numerous recent studies have applied fMRI to uncover highly stable resting state and task-related networks in healthy subjects by demonstrating correlated slow fluctuations of the BOLD signal across different brain regions (Raichle 2010; Engel et al. Neuron 2013). Applying this approach to MS patients, a couple of studies have demonstrated changes of coupling in networks relating to cognitive and sensorimotor functions (Roosendaal et al 2010; Faivre et al 2012). And we have recently shown that, in early-stage MS, cognitive decline is associated with increased

resting state coupling despite beginning structural desintegration of cortico-cortical networks (Hawellek et al 2011).

Functional reorganization has been extensively studied in MS by task-specific fMRI with remaining challenges regarding the interpretation of coactivation as compensatory or decompensatory (Filippi and Rocca 2011; Penner et al 2006). Therefore task-fMRI might be a sensitive outcome measure for short-term interventions.

Magnetoencephalography (MEG) provides the best currently available non-invasive method able to capture the spatiotemporal dynamics of brain networks. Using MEG it becomes possible to study local activity and large-scale interactions across a broad range of time scales and in a spectrally resolved manner (Engel et al. Neuron 2013). In particular, changes in power and coherence of fast oscillations at beta-band and gamma-band frequencies can be revealed (Hipp et al 2011) which are known to be closely related to cognitive processing (Engel et al 2001; Womelsdorf et al 2007; Senkowski et al 2008; Siegel et al 2012).

At present, almost nothing is known about the effects of MS pathology on the spatiotemporal CNS network dynamics and no information is available regarding changes over time or in response to an intervention such as exercise.

7 Objectives: Specific objectives or hypotheses

This study aims to explore the potential of an aerobic exercise program on brain structure and function in MS in a single-blind, randomized controlled phase IIa trial. We hypothesize that exercise will improve verbal learning and memory (primary endpoint) as well as induce changes in neuroimaging markers of structural and functional CNS connectivity (secondary endpoints). Tertiary outcomes will include walking ability, motor function and coordination, as well as patient-based outcomes (depression, fatigue, and health-related quality of life).

8 Trial design: Description of trial design including type of trial (eg, parallel group, crossover, factorial, single group), allocation ratio, and framework (eg, superiority, equivalence, noninferiority, exploratory)

This is a single-blind, randomized, controlled phase IIa trial with a parallel group design comparing 3 months of standardized aerobic exercise training (bicycle ergometry) to a waitlist control group (superiority framework). The allocation ratio of exercise to waitlist control is 1:1. The trial consists of a **primary trial phase** and an **extension phase** (see Figure 1). All primary analyses of endpoints will be restricted to the primary trial phase.

All outcome parameters will be assessed at baseline (week 0), after the intervention (month 3), and at follow-up (month 6), see Figure 1. Each outcome

assessment block (blue rectangles) includes: Clinical assessment (neurological scoring and neuropsychological testing), magnetic resonance imaging (structural and functional MRI), magnetencephalography (MEG), and assessments of physical fitness at the Department of Sports Medicine. After completing Month 3 assessments, patients randomized to the WLC will be offered the aerobic exercise training program and patients in the training group will be offered to continue the training free of charge (extension phase).

III) Methods: Participants, interventions, and outcomes

9 Study setting: Description of study settings (e.g., community clinic, academic hospital) and list of countries where data will be collected. Reference to where list of study sites can be obtained

This single-center study will be conducted at the University-Medical Center

Hamburg Eppendorf (UKE).

10 Eligibility criteria: Inclusion and exclusion criteria for participants. If applicable, eligibility criteria for study centers and individuals who will perform the interventions (e.g., surgeons, psychotherapists)

10.1. Patient inclusion criteria

- Relapsing-remitting patients according to McDonald (2010) criteria.
- Currently in remission
- Disease duration < 10 years
- Low to moderate physical disability (EDSS \leq 3.5)
- On stable immunotherapy > 3 months or without any planned treatment for the next year.

To determine the individual level of aerobic fitness, all patients will undergo a bicycle spiroergometry using the Metalyser 3b (CORTEX Biophysik GmbH, Leipzig, Germany). This test will be used as the anchor for the individualized training program (see below) as well as to monitor changes in aerobic fitness after the training intervention. The spiroergometry test starts with a resting-phase of 2 minutes. Ergometry will start at 25 Watts and performance will be continuously increased by 1 Watt every 4.8 seconds according to the WHO protocol (resulting in a ramp of 25 Watts/2min). We will continuously obtain stress ECG to monitor cardiovascular function (blood pressure (BP) and heart rate). Oxygen consumption will be recorded using the Metalyser 3b. In addition, blood draws for lactate assessment will be obtained with capillary pipettes (10µl) from one ear every 2 minutes and lactate values quantified by Biosen C-Line (EKF-diagnostic GmbH, Magdeburg, Germany). In addition, subjective exhaustion will be monitored by the Extended Borg scale (6-20) every 2 minutes. Patients will exercise under supervision until exhausted (Borg score of 18-20). Reasons for stopping (f.e. muscular fatigue, dyspnea) will be documented. For safety reasons, ergometry will also be stopped if a patient reaches systolic BP \ge 200 and/or diastolic BP \ge 110. If substantial ectopic electric heart activity or other complications occur, the spiroergometry will be stopped and the patient will be excluded from the study. After termination of the exhaustion test, spirometric data will be recorded for another 5 minutes. Lactate will be assessed after 1, 3, and 5 minutes during the cool-down period to detect the maximal lactate value. Two experienced exercise physiologists will determine the thresholds on the plots using semi-automated algorithms and blinded to patient identity. The Lactate thresholds AT and MaxLaSS will be determined using the first uptick in the lactate curve as well as the maximum change in lactate incline. Ventilatory thresholds 1 and 2 will be determined on the ventilation curve and confirmed by curves of ventilatory equivalents for O₂ (VE/VO₂), CO₂ (VE/VCO₂), and the slopes of VE and VCO₂, respectively (Wasserman et al., 1973). The maximum VO₂ value (ml \cdot kg⁻¹ \cdot min⁻¹) will be obtained close to exhaustion and will be considered as VO_{2peak}. The **anchor value** for the individually tailored exercise training will be the power (in Watts) recorded at Extended Borg scale score of 11.

10

11a.2. Individualized training plan

Training plan overview: The predefined training structure was designed to achieve a continuous increase of performance from training session (TS) to training session. Each training session consists of 3-5 intervals of training with interspersed breaks. The goal for every TS is to increase performance while keeping the level of perceived (Borg scale) and objectively measured exhaustion (heart rate) constant. Borg ratings will be averaged across all intervals of a given session (using the abbreviated Borg Scale 1-10). The following formula will be used to determine the starting training session (TS): ((Max performance [W] during spiroergometry / body weight [kg]) * 10) - 9. For example, a patient with a body weight of 80kg who reaches 240W in the spiroergometry will start training at: ((240 / 80) * 10) -9= 21, i.e. trainings session 21 (TS20). Each subsequent training session will increase duration as well as work load during each interval in a predefined manner (see Table 1).

Training	Interval #	Duration	Intensity	Performance (W)	Energy expended
Session #		(min)	(% of anchor value)		
TS 10	1	5	100	60	300
	2	6	100	60	360
	3	6	100	60	360
	4	6	100	50	300
	5	4	100	50	200
Total		27 min			91.200 Joule
TS 20	1	5	110	66	330
	2	10	120	72	720
	3	10	120	72	720
	4	10	110	66	660
	5	6	120	72	432
Total		41 min			171.720 Joule
TS 30	1	8	110	66	528
	2	10	120	72	720
	3	15	120	72	1080
	4	10	120	72	720
	5	10	110	66	660
	6	8	110	66	528
Total		61 min			254.160 Joule
TS 40	1	12	120	72	864
	2	15	130	78	1170
	3	15	150	90	1350
	4	15	140	84	1260
	5	12	120	72	864
Total		69 min			330.480 Joule

TABLE 1. Selected training sessions (TS) from the training plan including an example of calculated performance and energy expended for a hypothetical patient with an anchor value of 60W (in red).

Advancing through the training plan: Each interval of each training session (TS) will be Borg-rated (abbreviated Borg scale 1-10) and scores averaged across the TS. If the patient reaches an average Borg rating of 8 for the current session, the current level (e.g. TS10) will be repeated for the next session. Average Borg rating between 1 and 7 will result in advancing to a higher level. Average Borg ratings of 9 or 10 will result in

decreasing the training intensity for the next session. If a patient is unable to complete all required intervals of a given session, he or she will drop back to the last fully completed TS in the training program. The algorithm for determining the next training session intensity is illustrated in Figure 2.

The maximum length of any TS is 70

minutes (TS44). If a patient reaches TS44 (5 intervals: 10, 15, 15, 15 and 15 minutes with an intensity of 120, 140, 150, 150, and 150% power), they will repeat this level of intensity until the end of the 3 month training period.

Training sessions will be scheduled individually for each patient at the UKE Dept Physiotherapy and can be completed at the patient's convenience within the regular business hours Monday-Friday depending on the availability of training slots. During these times, experienced physiotherapists familiar with the AERCONN training program are available to supervise the training of the patients.

11 b: Explanation for choice of comparators:

The training will be compared to a wait-list control group which will receive the intervention after 6 months and a second ergometry was performed. We decided not to

use a sham-intervention because the effort of 2-3 sessions for three months is not to be justified based on ethical reasons for controls.

11 c: Criteria for discontinuing or modifying allocated interventions for a given trial participant (e.g., drug dose change in response to harms, participant request, or improving/worsening disease).

As a safety measure, spiroergometry will be stopped if a patient reaches systolic BP \geq 200 and/or diastolic BP \geq 110. If substantial ectopic electric heart activity or other complications occur, the spiroergometry will be stopped and the patient will be excluded from the study. Similarly, if any of these complications arise during the training program, the patient might be removed from the study due to safety concerns. This decision will be made after discussing the issue between the patient and the medical team (neurologist, exercise physiologist, physiotherapist).

Any patient might be excluded from the study when the training will be interrupted or was interrupted for more than 2 weeks or if training was reduced to one session/week for more than 2 weeks. Furthermore, patients experiencing persistent worsening of symptoms after training sessions lasting to the following day will be excluded.

11 c: Strategies to improve adherence to intervention protocols, and any procedures for monitoring adherence (e.g., drug tablet return; laboratory tests).

We will obtain detailed information about each patient's time constraints and other commitments before inclusion to avoid drop-outs due to logistical difficulties. Particular attention will be given to potential problems with transfers to the study site and back. In addition, patients will be informed that symptoms might reappear or temporarily worsen during or soon after training sessions. Early telephone calls after 2-4 weeks of training will be used to detect barriers for adherence. During the last 2 weeks of training, a structured interview focusing on exercise motivation and barriers will be conducted with each participant. This interview will be repeated at month 6. Patients will also receive a summary feedback regarding their individual response to treatment with respect to physical fitness and clinical parameters.

11d: Relevant concomitant care and interventions that are permitted or prohibited during the trial.

In case of deterioration such as a relapse during the training program, the participant is requested to contact the study center and to discuss treatment option (e.g. steroid treatment) and / or training interruption. Steroid treatment of relapses and an interruption of the training of up to 2 weeks will be tolerated. Longer interruptions will be considered breach of protocol and the patient excluded from the per-protocol analysis (but retained in the intention-to-treat analysis).

12 Outcomes: Primary, secondary, and other outcomes, including the specific measurement variable (e.g., systolic blood pressure), analysis metric (e.g., change from baseline, final value, time to event), method of aggregation (e.g., median, proportion), and time point for each outcome. Explanation of the clinical relevance of chosen efficacy and harm outcomes is strongly recommended.

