Interested patients will first be contacted by telephone to screen eligibility. Eligible patients will then be enrolled in the study and baseline assessment appointments will be scheduled. All outcome parameters will be assessed at month 0 (baseline) and month 3 (post intervention). *Each of these assessment blocks* includes 5 separate days of assessment (see Figure 3): *Day 1*: Visit to the MS outpatient center for neurological scoring, neuropsychology etc; *Day 2*: Visit to the Dept Neurophysiology for MEG. *Day 3* and Day 4: Visit to the Dept Neuroradiology for MRI. *Day 5*: Visit to the Dept Sports

Medicine for spiroergometry etc. During the entire assessment block (approx 7 days), the patients will wear the Actibelt® accelerometer. Randomization will be performed AFTER completion of day 5 in assessment block Wk 0.

Day 1 Assessment plan: During the clinical visit to the MS Center of the UKE, the following steps will be completed: Informed consent, blood sample (10 min), demographics

and EDSS (10 min), patient selfreport questionnaires (IDS-30SR, HAQUAMS, FSMC, MSWS-12, 30 min), neuropsychological testing battery (90 min), 9-HPT (5 min), 6MWT and T25 (10 min), MASC (20 min).

Day 2: MEG

assessments.

Day 3: Structural MRI assessments.

Day 4: Functional MRI assessments. Day 4 will only be done in 1/3 of the participants (i.e. the first 20 patients who

enter the trial).

(see inset).

Day 5 Assessment plan: The following assessments are conducted at the Dept Sports Medicine (in this order): Height and weight measurement (3 min), resting ECG (4 min), Bioelectrical Impedance Analysis (BIA, 6 min), spiroergometry (including blood draws before and after, 5ml plasma EDTA each, approx. 35 min), MFT-S3 assessment of balance and trunk stability (12 min), strength assessment (35 min), additional questionnaires (IPAQ (Lee 2011), Stadienzugehörigkeit im Transtheoretischen Modell (Basler 1999), Intention und Sportbezogene Selbstkonkordanz (Seelig & Fuchs 2006), Sportbezogene Konsequenzerwartung (Fuchs 1994), Sportbezogene Situative Barrieren und Management (Krämer & Fuchs 2010), sportbezogene sozialen Unterstützung (Fuchs 2008), Sportbezogene Selbstwirksamkeit (approx. 30 min)).

14 Sample size: Estimated number of participants needed to achieve study objectives and how it was determined, including clinical and statistical assumptions supporting any sample size calculations

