Sample size was calculated based on results obtained in the pilot study on exercise and cognitive function in progressive MS (Briken et al., MSJ 2013). Below are the power calculations for the VLMT learning (trials 1 through 5) and delayed memory (trial 7).

14.1. VLMT Learning:

Numeric Results for Two-Sample T-Test

Null Hypothesis: Mean1=Mean2. Alternative Hypothesis: Mean1<>Mean2

The standard deviations were assumed to be unknown and equal.

Power	N1	N2	Ratio	Alpha	Beta	Mean1	Mean2	S1	S2
0.90388	20	20	1.000	0.02500	0.09612	4.0	9.8	5.0	5.0
0.81609	16	16	1.000	0.02500	0.18391	4.0	9.8	5.0	5.0
0.90639	17	17	1.000	0.05000	0.09361	4.0	9.8	5.0	5.0
0.80985	13	13	1.000	0.05000	0.19015	4.0	9.8	5.0	5.0

Group sample sizes of 20 and 20 achieve 90% power to detect a difference of -5.8 between the null hypothesis that both group means are 4.0 and the alternative hypothesis that the mean of group 2 is 9.8 with estimated group standard deviations of 5.0 and 5.0 and with a significance level (alpha) of 0.02500 using a two-sided two-sample t-test.

14.2. VLMT Delayed recall:

Numeric Results for Two-Sample T-Test

Null Hypothesis: Mean1=Mean2. Alternative Hypothesis: Mean1<>Mean2

The standard deviations were assumed to be unknown and equal.

Power	N1	N2	Ratio	Alpha	Beta	Mean1	Mean2	S1	S2
0.91886	17	17	1.000	0.02500	0.08114	0.6	3.2	2.0	2.0
0.81514	13	13	1.000	0.02500	0.18486	0.6	3.2	2.0	2.0
0.91148	14	14	1.000	0.05000	0.08852	0.6	3.2	2.0	2.0
0.82630	11	11	1.000	0.05000	0.17370	0.6	3.2	2.0	2.0

Group sample sizes of 17 and 17 achieve 92% power to detect a difference of -2.6 between the null hypothesis that both group means are 0.6 and the alternative hypothesis that the mean of group 2 is 3.2 with estimated group standard deviations of 2.0 and 2.0 and with a significance level (alpha) of 0.02500 using a two-sided two-sample t-test.

14.3. Summary statement:

Based on these calculations, powering for the dual primary endpoints VLMT learning and VLMT delayed recall, 90% power will be achieved with n=20 patients in each

arm of the trial. To safeguard against dropouts (based on previous experience, drop-out in behavioral trials often reach 20%) and the possibility that effect sizes in the pilot trial may have overestimated the real effect, we will enrol n=60 patients in the trial so that we will have approximately n=30 in each trial arm.

15 Recruitment: *Strategies for achieving adequate participant enrolment to reach target sample size.*

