Management of screening, inclusion and study conduct will be based on the internet-based project-management tool attached to the HAPIMS database. This database uses secure data management and has been approved for use by the responsible Data Protection and Security Office of the UKE. Data will be collected on paper-based source documents (neuropsychological assessments, performance-based measures, questionnaires) or primary computer-based (MRI, MEG) or chip-based (accelerometry). Data will be uploaded on a protected web-based project-platform to allow an integrated view on all assessments.

Assessment of safety: DSMB reports will be prepared biannually. As we do not expect adverse events DSMB recommendations for taking patients out or stopping the study seem highly unlikely.

18b Retention: Plans to promote participant retention and complete follow-up, including list of any outcome data to be collected for participants who discontinue or deviate from intervention protocols.

See 11c.

19 Data management: *Plans for data entry, coding, security, and storage, including any related processes to promote data quality (e.g., double data entry; range checks for data values).* Reference to where details of data management procedures can be found, if not in the protocol.

Data-input from source documents will be double-checked by 2 persons.

20 Statistical methods

20a: Statistical methods for analyzing primary and secondary outcomes. Reference to where other details of the statistical analysis plan can be found, if not in the protocol.

The primary analyses will compare changes from Month 0 to Month 3 between the exercise group and the waitlist control group. According to guidelines for statistical analysis of clinical trials published by The European Agency for the Evaluation of Medicinal Products (CPMP/ICH/363/96 and CPMP/EWP/2863/99), we will computed the primary statistical analysis for all outcomes using ANCOVA models adjusting for baseline measurements of the respective outcome variable to evaluate treatment effects (measured

as change from baseline). No other covariates will be included in this primary analysis. As recommended, this model will also not include treatment by covariate interactions.

All primary analyses will be conducted as intention-to-treat (ITT) including all patients who have received group allocation. Every effort will be made to obtain Month 3

Wk 0	Mo 3		Mo 6

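### Section 11c lets staff exclude randomised patients from the study on training-related triggers that only the exercise arm can meet before Month 3, against the follow-up promised in 20a

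*Protocol*

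**What the plan says.** The first of the two items numbered 11c in the protocol (criteria for discontinuing or modifying the allocated intervention) contains four triggers tied to training:

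- Interruption: "Any patient might be excluded from the study when the training will be interrupted or was interrupted for more than 2 weeks".
- Reduction to one session a week for more than 2 weeks, in the same sentence and with the same consequence.
- Complications: "Similarly, if any of these complications arise during the training program, the patient might be removed from the study due to safety concerns". The decision follows discussion between the patient and the medical team.
- Next-day worsening: "patients experiencing persistent worsening of symptoms after training sessions lasting to the following day will be excluded". This one is mandatory, and the sentence does not say what the patient is excluded from.

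Three other sections bear on the same patients:

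- Section 11d, on events introduced by "In case of deterioration such as a relapse during the training program", says of breaks beyond 2 weeks: "Longer interruptions will be considered breach of protocol and the patient excluded from the per-protocol analysis (but retained in the intention-to-treat analysis".
- Section 20a defines the primary analysis as intention-to-treat (ITT) in all allocated patients. It promises every effort to obtain Month 3 and Month 6 data, including from those who drop out of the exercise programme, and uses LOCF where data are missing.
- Section 18b, whose item text asks for a "list of any outcome data to be collected for participants who discontinue or deviate from intervention protocols", answers only with a reference to 11c. Neither item with that number lists such data.

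**The concern.** Randomisation comes before training (section 13: "Randomization will be performed AFTER completion of day 5 in assessment block Wk 0"). Waitlist patients train only after the Month 3 assessments (section 8) or after 6 months (section 11b). On either statement, a rule that depends on training can remove only exercisers before the primary endpoint. It is therefore a post-randomisation exclusion, linked to adherence and tolerability, that operates in one arm.

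Section 20a would keep these patients and measure them. A site that follows 11c literally would not bring them back for Month 3. Their VLMT change would then be imputed as zero, while controls keep whatever gain they show on retesting. The primary comparison would carry avoidable missing data in one arm, and no later analysis plan can recover visits that did not take place.

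**Working it through.** **1. The sections side by side**

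| Event in an exerciser | First item 11c | 11d | 20a |
|---|---|---|---|
| Training break over 2 weeks | may be excluded from the study | after deterioration such as relapse: out of per-protocol, kept in ITT | kept, outcomes sought |
| One session a week for over 2 weeks | may be excluded from the study | not covered | kept, outcomes sought |
| Complication during training | may be removed from the study | covered only if it is a deterioration that leads to a break over 2 weeks | kept, outcomes sought |
| Worsening to the next day | will be excluded (object not stated) | covered only if it leads to a break over 2 weeks | kept, outcomes sought |

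The spiroergometry stopping sentence in 11c is not part of this point. At baseline the test precedes randomisation. At Month 3 it falls on Day 5, after the VLMT on Day 1.

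**2. Inputs for the illustration**

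- Section 14.1, learning: mean change 4.0 (control) and 9.8 (exercise), SD 5.0.
- Section 14.2, delayed recall: 0.6 and 3.2, SD 2.0.
- Two-sided alpha 0.025, and about 30 per arm (14.3).
- Assumed, because the protocol gives no exclusion rate: k = 1, 2, 3, 6 or 9 of 30 exercisers excluded and no missing data among controls. The one related figure is the 20% drop-out in 14.3, which is for any cause and not split by arm.

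**3. The plan's own figures**

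Two-sample t-test power from the noncentral t distribution gives 0.90388 for learning at 20 per arm and 0.91886 for recall at 17 per arm. Both match the protocol. At 30 per arm with no exclusions, power is 0.984 (learning) and 0.996 (recall).

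**4. Formulas**

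Let p = k/30, m0 and m1 the control and exercise means, and s the SD.

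- LOCF (excluded patients get change 0): difference = (1−p)·m1 − m0; exercise-arm variance = (1−p)·s² + p(1−p)·m1².
- Followed and control-like (excluded patients are measured and change as controls do): difference = (1−p)·(m1−m0); exercise-arm variance = s² + p(1−p)·(m1−m0)².
- Pooled variance = mean of the exercise-arm variance and s².
- Loss caused by LOCF = second difference minus first = p·m0.

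Example, learning, k = 3 (p = 0.1):

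- LOCF difference = 0.9 × 9.8 − 4.0 = 4.82. Exercise-arm variance = 0.9 × 25 + 0.09 × 96.04 = 31.14. Pooled SD = √((31.14 + 25)/2) = 5.30. Power 0.886.
- Followed difference = 0.9 × 5.8 = 5.22. Power 0.945.
- Loss = 0.1 × 4.0 = 0.40 points.

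**5. Results, 30 per arm**

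| Excluded | Learning, LOCF: difference (power) | Learning, followed: difference (power) | Loss | Recall, LOCF: difference (power) | Recall, followed: difference (power) | Loss |
|---|---|---|---|---|---|---|
| 1 | 5.47 (0.965) | 5.61 (0.975) | 0.13 | 2.49 (0.992) | 2.51 (0.993) | 0.02 |
| 2 | 5.15 (0.933) | 5.41 (0.962) | 0.27 | 2.39 (0.985) | 2.43 (0.987) | 0.04 |
| 3 | 4.82 (0.886) | 5.22 (0.945) | 0.40 | 2.28 (0.974) | 2.34 (0.979) | 0.06 |
| 6 | 3.84 (0.658) | 4.64 (0.864) | 0.80 | 1.96 (0.902) | 2.08 (0.927) | 0.12 |
| 9 | 2.86 (0.380) | 4.06 (0.738) | 1.20 | 1.64 (0.757) | 1.82 (0.825) | 0.18 |

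The effect of 11c is the gap between the LOCF and followed columns, not the gap from 5.8 or 2.6.

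**6. The other direction**

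If the excluded patients would have changed by c, LOCF shifts the difference by −p·c. With c = −2 on learning (assumed), it overstates the benefit by 2p = 0.07, 0.13, 0.20, 0.40 and 0.60 points for k = 1, 2, 3, 6 and 9.

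**The case against.** The strongest reply is that the protocol already answers the question. The heading of 11c concerns the allocated intervention, the item does not say that outcome collection stops, and 20a states the rule on follow-up and analysis outright. If exclusion in 11c is read as stopping training, then 11c, 11d and 20a agree. Three of the four triggers are discretionary, and the mandatory one names no object, so staff can comply with both sections. This reading is possible, and 20a and 11d probably show what was intended. But 11c speaks of exclusion or removal from the study, whereas 11d names an analysis set when it means one. Section 18b sends the reader back to 11c, not to 20a. Discretion does not help either: optional removal after randomisation, in one arm, is still a route to bias.

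Second, 20a plans a rank-based ITT sensitivity analysis that gives drop-outs the lowest rank. If excluded exercisers count as drop-outs, it guards against LOCF flattering exercise. It does not recover the lost values, and it does not correct a bias against exercise.

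Third, the larger rows of the table assume 20 to 30% exclusion in one arm with complete data in the other, which nothing in the protocol supports. The calculation also uses a t-test, while the planned analysis is a baseline-adjusted ANCOVA. Both points stand. The figures are an illustration, and at 1 or 2 exclusions power stays above 0.90 on both endpoints.

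**Conclusion.** The concern holds. The wording of 11c conflicts with 20a for all four training triggers, and with 11d for breaks over 2 weeks after a deterioration. Before Month 3 it can act on the exercise arm only. LOCF affects any missing value; what 11c adds is missingness in one arm that could be avoided.

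The size is unknown because no exclusion rate is given. Under the protocol's own means and SDs, with controls complete, the loss on learning is 0.13 to 0.40 points for 1 to 3 exclusions and 0.80 points for 6. Recall loses no more than 0.12 points over the same range. These figures assume that the excluded patients would have changed like controls. The sign reverses if they would have declined. The point should be fixed because it concerns the primary randomised comparison and the correction is cheap, not because a large effect has been shown.

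**What to change.** In the first item 11c, for randomised patients, replace exclusion or removal from the study, and the unqualified exclusion for next-day worsening, with discontinuation from training and from the per-protocol set. Leave the clinical stopping criteria and the medical-team decision as they are. Add a sentence: *These patients keep the Month 3 and Month 6 assessments, with spiroergometry omitted where contraindicated, and are analysed as randomised.* Change 18b to point to that sentence and to 20a, and give the two items numbered 11c separate numbers so that the reference is unambiguous.

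The cost is protocol wording, since the assessment visits are already scheduled. It will take modest effort to bring back patients who have stopped training, and some may decline.
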